5.1 Schedule

The responsible doctor will conduct observations and examinations according to the following schedule. The results should be described in the case report.

	Run in period (Visit 1) ^{*3}	Treatment phase 1 (short-term effects)		Treatment phase 2 (long-term effects)		
		Visit2 ^{*4}	Visit3	Just before the start	8 weeks later	52 weeks later
Subject background		●				
Height ^{*1} , weight, abdominal circumference ^{*1}		●	●	●	●	
Blood pressure, pulse rate		●	●	●	●	
AST, ALT, TC ^{*5} , LDL ^{*5} , HDL ^{*5} , TG ^{*5} , serum uric acid, HbA1c, GLU, serum creatinine ^{*2}	● ^{*3}		●	●	●	
Na, K, Cl						
Plasma XO Activity			●	●	●	
Inflammatory Markers			●	●	●	
Oxidative Stress Markers			●	●	●	
Urinary angiotensinogen			●	●	●	
Urinary L-FABP			●	●	●	
urinalysis	●	●	●	●	●	
Medication status of research drugs				●	●	
Concomitant medications			●	●	●	
adverse event						→

^{*1} Height and abdominal circumference can be measured once during the study participation period.

^{*2} Calculate eGFR using the estimation formula of the Japanese Society of Nephrology.

^{*3} Test results within 4 weeks before the time of eligibility determination shall be made available.

Visit 3 test results will be available within 2 weeks before and after the test.

Visit 4 test results will be available within 4 weeks before and after the test.

After final eligibility confirmation, serum uric acid levels below 7.0 mg/dl will not be entered into the treatment phase.

If there is no value measured by a medical institution, the value is automatically calculated by a formula:

$$TC-HDL-C-(TG/5)=LDL-C$$

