5.2 Survey items

(1) Background of subjects

The following items shall be investigated when determining eligibility.

Age, gender, CKD stage, blood pressure, renal function, pre-existing conditions, and complications

(2) Height, weight, and abdominal circumference

Weight will be measured when determining eligibility, before the start of each treatment period, and after each treatment period. Height will be measured once during the study participation period. Concurrent pharmaceuticals (antihypertensive agents, diuretics, antidiabetic agents, lipid agents, basic renal failure agents)

(3) Blood pressure and pulse rate

At the time of eligibility determination, before the start, and after each treatment period, blood

pressure, and pulse rate will be checked after resting in a sitting position for 5 minutes.

(4) Blood test, renal function

The following items will be measured when determining eligibility determination, Run period, and moments before, 8W after, and 52W after initiation of therapeutic agents. When determining eligibility, test results from 4 weeks before the time of eligibility determination will be available for the determination.

AST, ALT, TC, LDL, HDL, TG, serum creatinine, Na, K, Cl, serum uric acid, HbA1c, GLU
Calculate the eGFR using the following formula13).

eGFR (mL/min/1.73m²)=194 x Cr^{-1.094} x Age^{-0.287} (x 0.739 for women)

(5) Plasma XO activity

Measurements will be taken shortly before the start of therapeutic agents, 8W after the start, and 52W after the start. For measurement, samples are frozen at -80°C, and batch measurement is conducted when the number of samples is available.

(6) Inflammatory markers, oxidative stress markers, renal RA system markers, and tubulointerstitial damage markers

Measurements will be taken shortly before therapeutic agents begin, 8W after the start, and 52W after the start. Samples will be frozen at -80°C for measurement, and batch measurement will be conducted when the number of samples is adequate. Among the following items, inflammatory markers, oxidative stress markers, and urinary L-FABP will be assessed by SRL Co.

Inflammatory markers: high sensitivity CRP

Oxidative stress markers:

Urinary 8-OHdG (8-hydroxy-2'-deoxyguanosine)

Urinary angiotensinogen

Urinary L-FABP

(7) Urinalysis (microalbuminuria and urine pH, urine Na, urine UA)

(Early morning) Use urine as needed. (Early morning) Use urine as needed.

(8) Inspection for safety confirmation

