- (11) Patients who have participated in other clinical studies (including clinical trials) within 6 months prior to eligibility determination
- (12) Patients with urinary tract stones
- (13) Other patients whom the physician in charge judges to be unsuitable as subjects.
- (14) Patients with serum uric acid levels below 7.0 mg/dl in the post-visit 2 lifestyle guidance phase will not be randomized to the treatment phase. (Final eligibility check)
- (15) Patients with a history of acute myocardial infarction, acute coronary syndrome, intervention for coronary artery stenosis (catheterization and coronary artery bypass surgery), ventricular tachycardia, multisource ventricular arrhythmia, or acute heart failure within 3 months prior to the time of eligibility determination (newly added based on the results of the CARES study)

2-3. Study design

A multi-center, randomized, parallel-group comparison trial

2-4. Random allocation

Participants will be randomly allocated to:

Treatment group A (lifestyle guidance + benzbromarone) or

Treatment group B (lifestyle guidance + febuxostat)

2-5. Research treatment

URAT 1 inhibitor: benzbromarone (Urinorm® tablet)

Xanthine oxidase inhibitor: febuxostat (Feburic® Tablets)

2-5-1. Run in period

During the Run in phase (8 weeks), lifestyle guidance (diet, restriction of alcohol consumption, exercise recommendations, etc.) will be given with reference to the Guidelines for the Treatment of Hyperuricemia and Gout (2nd edition).

2-5-1. Treatment period 1

After final eligibility determination, febuxostat 10 mg/day or benzbromarone 25 mg/day will be administered in treatment phase 1 after confirming tolerability in addition to lifestyle guidance. The dose of febuxostat will be increased to 20 mg/day from week 5. The duration of treatment should be 8 weeks.

2-5-2. Treatment period 2

The medication used in treatment phase 1 should be adjusted to achieve a serum uric acid level of less than 6 mg/dl. The treatment period should be 44 weeks (1 year from the start of the drug).

2-6. Endpoint

2-6-1. Primary endpoint for efficacy

Change in eGFR from immediately before initiation of randomized treatment (visit2) to 52 weeks after initiation of treatment (visit 4):

(eGFR at visit 4 – eGFR at visit2) / eGFR at visit 2 [unit: % / 52 weeks] and
eGFR at visit 4 – eGFR at visit 2 [unit: ml / min / 1.73m² / 52 weeks]

2-6-2. Secondary endpoint for efficacy

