- (1) Change in eGFR from immediately before initiation of randomized treatment (visit2) to 8 weeks after initiation of treatment (visit 3) [unit: % / 52 weeks and ml / min / 1.73m² / 8 weeks]
- (2) Change in office blood pressure from immediately before initiation of randomized treatment (visit2) to 8 & 52 weeks after initiation of treatment (visits 3 & 4) [unit: % / 8 weeks, % / 52 weeks, mmHg / 8 weeks and mmHg / 52 weeks]
- (3) Difference in change in eGFR from immediately before initiation of randomized treatment (visit2) to 8 weeks after initiation of treatment (visit 3) (per 4 weeks) and change in eGFR from 8 weeks to 52 weeks after initiation of treatment (visit 4) (per 4 weeks) [unit: % / 4 weeks and ml /min / 1.73m² / 4 weeks]

Difference in change in eGFR from immediately before initiation of randomized treatment (visit2) to 52 weeks after initiation of treatment (visit 4) (per 4 weeks) and change in eGFR from initiation of run-in period (visit 1) to initiation of randomized treatment (visit 2) (per 4 weeks) [unit: % / 4 weeks and ml /min / 1.73m² / 4 weeks]

Difference in change in eGFR from 8 weeks (visit 3) to 52 weeks after initiation of treatment (visit 4) (per 4 weeks) and change in eGFR from initiation of run-in period (visit 1) to initiation of randomized treatment (visit 2) (per 4 weeks) [unit: % / 4 weeks and ml /min / 1.73m² / 4 weeks]

- (4) Change in serum uric acid level from immediately before initiation of randomized treatment (visit2) to 8 & 52 weeks after initiation of treatment (visits 3 & 4) [unit: % / 8 weeks, % / 52

weeks, mg / dl / 8 weeks and mg / dl / 52 weeks]

Rate of attainment of serum uric acid level <6.0 mg/dl at 8 & 52 weeks after initiation of treatment (visits 3 & 4) [unit: %]

(5) Change in urinary albumin / creatinine ratio from immediately before initiation of randomized treatment (visit2) to 8 & 52 weeks after initiation of treatment (visits 3 & 4) [unit: % / 8 weeks, % / 52 weeks, mg / gCr / 8 weeks and mg / gCr / 52 weeks]

(6) Change in urine pH from immediately before initiation of randomized treatment (visit2) to 8 & 52 weeks after initiation of treatment (visits 3 & 4) [unit: % / 8 weeks, % / 52 weeks, absolute change / 8 weeks and absolute change / 52 weeks]

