4.1. Handling of follow-up survey results

Survey will be conducted at initiation of run-in period (visit 1), immediately before initiation of randomized treatment (visit 2), and 8 & 52 weeks after initiation of treatment (visits 3 & 4). Visit 3 survey results within 2 weeks of the planned visit will be used for statistical analysis and visit 4 survey results within 4 weeks of the planned visit will be used for statistical analysis. When participants are complicated with concomitant disease which can affect eGFR, survey results after onset of the disease will be deleted as missing values.

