5.4. Primary analysis

Change in eGFR from immediately before initiation of randomized treatment (visit2) to 52 weeks after initiation of treatment (visit 4):

(eGFR at visit 4 – eGFR at visit2) / eGFR at visit 2 [unit: % / 52 weeks] and

eGFR at visit 4 – eGFR at visit 2 [unit: ml / min / 1.73m² / 52 weeks]

will be estimated and compared between randomized groups using unpaired t-test or analysis of variance (ANOVA). Mean differences in eGFR change between randomized groups, 95% confidence intervals and p values will be estimated. If there is significant imbalance in important factors in baseline characteristics, analysis of covariance (ANCOVA) will be used as sensitivity analysis. If missing values in the primary outcome are observed among ≥5% of participants, multiple imputation will be conducted as sensitivity analysis. These results will be summarized in Table (Primary analysis).

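### The primary eGFR test, and the blood pressure, uric acid and albuminuria comparisons, leave the Visit 1 pre-drug value unused: lost precision, not bias

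*Protocol*

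**What the plan says.** SAP 2-6-1 defines the primary endpoint, in absolute and percent form, as "Change in eGFR from immediately before initiation of randomized treatment (visit2) to 52 weeks after initiation of treatment (visit 4"). SAP 5.4 states that the two forms "will be estimated and compared between randomized groups using unpaired t-test or analysis of variance (ANOVA"). Covariates enter only conditionally: "If there is significant imbalance in important factors in baseline characteristics, analysis of covariance (ANCOVA) will be used as sensitivity analysis". SAP 5.5.1 carries this approach over to the secondary outcomes, and the repeated-measures model in SAP 5.5.2 also works on change from Visit 2.

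Two pre-drug assessments exist. SAP 4.1 states: "Survey will be conducted at initiation of run-in period (visit 1), immediately before initiation of randomized treatment (visit 2"). For creatinine and uric acid, protocol 5.2(4) says "The following items will be measured when determining eligibility determination, Run period, and moments before, 8W after" start of drug. For blood pressure, protocol 5.2(3) says "At the time of eligibility determination, before the start, and after each treatment period". The schedule in protocol 5.1 also places urinalysis at Visit 1.

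Visit 1 eGFR does have one use. Two of the three parts of secondary endpoint (3) in SAP 2-6-2 subtract the "change in eGFR from initiation of run-in period (visit 1) to initiation of randomized treatment (visit 2) (per 4 weeks"). XO activity, hs-CRP, urinary 8-OHdG, angiotensinogen and L-FABP are first measured just before drug, so they have no Visit 1 value (protocol 5.2(5) and (6)).

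**The concern.** A single creatinine carries visit-to-visit error. In an unadjusted change score, the error in the Visit 2 value passes in full into each patient's 52-week change. The Visit 1 value tells something about the same patient's underlying level with a separate error, and it precedes study drug, so it can be used as a covariate without favouring either arm. The plan collects it and leaves it out of the main comparison.

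At stake is the width of the confidence intervals for the arm differences in eGFR, blood pressure, uric acid and albuminuria, in a trial whose size is fixed at 100. The only covariate model for the primary endpoint is reached if baseline imbalance is judged significant, so even the ordinary gain from adjusting for Visit 2 is not secured in advance.

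**Working it through.** **1. The plan's own figure.** Inputs from protocol 4.2: difference 15, SD 20, two-sided 5%, power 90%, drop-out 20%.
- Normal approximation: n = 2 × (1.960 + 1.282)² × 20² / 15² = 37.4, so 38 per arm. The t-test needs 39. Then 39 / 0.8 = 48.75, so 49 per arm and 98 in total, against the stated 100.
- With 50 × 0.8 = 40 evaluable per arm, power is 91.8% (normal) or 91.2% (t-test). The stated power is met on the stated inputs.

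**2. SD of the 52-week change.** The per-protocol rows of Supplementary Table 1 have half-widths of (4.03 − 0.69)/2 = 1.67 and (1.54 + 1.99)/2 = 1.765. SD = half-width / t × √n. The table gives no n per arm; at an assumed 40 to 50 this is 5.2 to 6.2. I use 5.8.

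**3. Visit-to-visit SD.** The documents do not give it. A rough figure comes from the first row of Supplementary Table 2, with half-widths 0.84 and 0.90. That row is (V4 − V2)/13 − (V2 − V1)/2. Suppose the run-in change is pure error, with t the error variance on the scale of the arm mean. The variance of the row is then V/169 + t/2 + t/13, where V is the variance of the mean 52-week change.
- Taking SE as half-width / 2, for 1.67 and 0.84: V = 0.697 and t = (0.1764 − 0.0041)/0.5769 = 0.299. At n = 40 the visit SD is √(40 × 0.299) = 3.5.
- Across the inputs, this route gives 3.5 to 4.2. It is too high if any run-in change is real. Assuming instead equal variance of change in run-in and early treatment, the Week 0–8 row gives 2.4 to 2.8.

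I take 2 to 3.5 as the working range.

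**4. Simulation for eGFR.** 40 per arm, change SD 5.8, patients selected on Visit 1 eGFR of 30 to 60. Entries are the cut in variance of the arm difference against the unadjusted change score.

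| Visit SD | True run-in change SD | Visit 2 only | Visit 2 + Visit 1 |
|---|---|---|---|
| 3.5 | 0 | 5% to 6% | about 17% |
| 3.5 | 2 | not tabulated | 14.7% |
| 3 | 0 | 2.4% | 10.4% |
| 3 | 2 | 2.4% | 9.1% |
| 2.5 | 2 | not tabulated | 4.8% |
| 2 | 2 | not tabulated | 1.5% |
| 2 to 2.5 | 4 | not tabulated | −0.6% to 1.6% |

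For visit SD 3 with no run-in change, the SEs are 1.308, 1.292 and 1.238, and 1 − (1.238/1.308)² = 10.4%. Over the whole range, Visit 2 alone gives about −1% to 7%. No bias appeared. At the top end, 1/(1 − 0.17) = 1.20, equivalent to 20 extra patients per 100; at the bottom, 1/(1 − 0.02) = 1.02, equivalent to 2.

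**5. Averaging is not a safe substitute.** With equal correlations r between visits, change from Visit 2 has variance 2(1 − r)σ² and change from the two-visit mean has 1.5(1 − r)σ², a 25% cut. If Visit 1 correlates with Visit 4 by 0.05 to 0.10 less than Visit 2 does (r 0.7 to 0.9), averaging gives 83% to 138% of the planned variance. The two-covariate model gives 77% to 95% in the same cases.

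**6. Systolic pressure, on assumed SDs only.** Take visit SD 8, between-patient SD 10, true-change SD 6.
- Change score: 2 × 64 + 36 = 164.
- Adjusted for Visit 2: 200 − 100²/164 = 139.0, a 15% cut.
- Adjusted for both: 200 − 100²/132 = 124.2, a 24% cut. Visit 1 takes about 11% off the Visit 2-adjusted variance.

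Over visit SD 8 to 10 and between-patient SD 10 to 12, the total cut is about 22% to 28%, and Visit 1 takes about 8% to 13% beyond Visit 2.

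**The case against.** The strongest reply is that change from the value immediately before drug is a valid, prespecified endpoint that separates the drug effect from the run-in, and that the planned size delivers its power with drop-out already counted. That stands. Nothing here is an error, and a reader who inferred that the comparison is biased or the trial underpowered for this reason would go beyond the documents.

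Visit 1 is also not a plain repeat of Visit 2. Eight weeks of lifestyle guidance lie between them, eligibility is judged on Visit 1, and protocol 5.1 allows older results: "Test results within 4 weeks before the time of eligibility determination shall be made available". Urate-lowering drugs are excluded only for the 2 weeks before eligibility, so an accepted uric acid result could have been drawn on such a drug. These features are common to both arms, so they shrink the gain without biasing the comparison. They are also why averaging is not recommended.

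A reader might infer that every change endpoint discards a Visit 1 value. It does not: five markers have none, and two parts of endpoint (3) use it. A reader might also infer that adjusting for Visit 2 achieves nothing because the change already subtracts it. That is wrong too. Adjusted for Visit 2, the change-score model gives the same arm effect as modelling Visit 4 with Visit 2 as covariate, and the Visit 2 error no longer passes through in full.

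Finally, the size is soft. The visit SDs are assumed, the simulation omits the allocation factors in protocol 4.3, and no figure is available for uric acid, albuminuria or percent change in eGFR. Titrating uric acid to below 6 mg/dL in period 2 probably weakens its link to baseline. This limits what can be promised, but does not remove the case for a change that costs almost nothing.

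**Conclusion.** The point holds as missed efficiency. For absolute eGFR change, the variance cut is about 2% to 17%, small to moderate, resting on 40 evaluable patients per arm, a change SD near 5.8, a visit SD of 2 to 3.5 and a true run-in change SD of 0 to 2 (all in mL/min/1.73m²). With a run-in change SD of 4 and a visit SD of 2 to 2.5, the gain is about nil and the loss at worst under 1%. The equivalent of 20 extra patients per 100 is the best corner of the range, not the expected gain. The 25% from averaging needs equal correlations between visits, which the documents do not establish. The blood pressure figures illustrate assumed SDs.

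**What to change.** Leave the endpoint as Visit 4 minus Visit 2. In SAP 5.4, replace the unadjusted test and the imbalance-triggered ANCOVA with one prespecified primary model: a linear model with arm, Visit 2 eGFR and Visit 1 eGFR. Where a Visit 1 value is missing, fill that covariate with its overall mean so that no patient is lost. In SAP 5.5.1, use the same form for office blood pressure, uric acid and the log urinary albumin/creatinine ratio, each with its own Visit 2 and Visit 1 values. Keep the unadjusted comparison as a supporting analysis. Do not replace Visit 2 by the mean of the two visits.

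The cost is SAP wording and at most two degrees of freedom; no new data are needed. Since results are already tabulated in the supplementary tables, any re-analysis on this model should be labelled post hoc.

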4.5 Combination therapy

In principle, the type, dosage, or administration of concomitant medications should not be changed during Treatment Periods 1 and 2. However, this does not apply to cases where intensification of treatment is required because of deteriorating renal or blood pressure function, or where changes in treatment are necessary to address other complications. Patients

receiving benz bromarone should be advised to drink water, and urine alkalinization should be considered if the patient's urine is acidic.

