(7) Change in XO activity from immediately before initiation of randomized treatment (visit2) to 8 & 52 weeks after initiation of treatment (visits 3 & 4) [unit: % / 8 weeks, % / 52 weeks, pmol IXP / min / mL / 8 weeks and pmol IXP / min / mL / 52 weeks]

(8) Change in hs-CRP from immediately before initiation of randomized treatment (visit2) to 8 & 52 weeks after initiation of treatment (visits 3 & 4) [unit: % / 8 weeks, % / 52 weeks, mg / dL / 8 weeks and mg / dL / 52 weeks]

(9) Change in urinary 8-OHdG (8-hydroxy-2'-deoxyguanosine) from immediately before initiation of randomized treatment (visit2) to 8 & 52 weeks after initiation of treatment (visits 3 & 4) [unit: % / 8 weeks, % / 52 weeks, ng / mL / 8 weeks and ng / mL / 52 weeks]

(10) Change in urinary angiotensinogen from immediately before initiation of randomized treatment (visit2) to 8 & 52 weeks after initiation of treatment (visits 3 & 4) [unit: % / 8 weeks, % / 52 weeks, μ g / gCr / 8 weeks and μ g / gCr / 52 weeks]

(11) Change in urinary L-FABP from immediately before initiation of randomized treatment (visit2) to 8 & 52 weeks after initiation of treatment (visits 3 & 4) [unit: % / 8 weeks, % / 52 weeks, μ g / gCr / 8 weeks and μ g / gCr / 52 weeks]

2-7. Sample size estimation

Expected number of participants: 100 (50 in each of treatment groups A and B)

[Rationale for sample size estimation]

The main objective of this study was to exploratively investigate the effect of febuxostat administration and benz bromarone on renal function in patients with hyperuricemia complicated by chronic kidney disease. Based on the results of previous studies, we expected the difference between the two treatments to be eGFR/52W 15 ml/min/1.73m².^{1,2} Then, we calculated α 0.05, power 0.8, δ 15, σ 20, and dropout rate as 20%.

2-8. Follow-up duration

Participants will be followed up for 52 weeks (treatment period 1 for 8 weeks and treatment period 2 for 44 weeks).

2-9. Research period

Research period: from approval by the Ethical Review Committee to February 28, 2021

Registration period : from approval by the Ethical Review Committee to November 30, 2018

3. Analysis population

Full analysis set (FAS): In accordance with the intention to treat (ITT) principle, all patients except for those without information after randomization will be included in the analysis.

Per protocol set (PPS): Sensitivity analysis excluding participants with protocol violation might be conducted.

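### Urinary 8-OHdG is defined in ng/mL while the other urinary markers are per gram creatinine, which leaves its between-arm comparison open to a dilution artefact because the only stated water advice is for benzbromarone patients

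*Protocol*

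**What the plan says.** SAP section 2-6-2 lists the secondary efficacy endpoints with their units. Item (9) is "9) Change in urinary 8-OHdG (8-hydroxy-2'-deoxyguanosine) from immediately before initiation of randomized treatment (visit2) to 8 & 52 weeks after initiation of treatment", with percent units and then "52 weeks, ng / mL / 8 weeks and ng / mL / 52 weeks". That is a concentration with no creatinine in the denominator.

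The other urinary markers in the same list are creatinine-corrected. Item (5), the albumin/creatinine ratio, is in "mg / gCr / 8 weeks and mg / gCr / 52 weeks". Items (10) and (11), angiotensinogen and L-FABP, are in µg per gCr. Protocol sections 0.6, 5.2 and 7.1 name 8-OHdG without giving a unit, so nothing elsewhere supplies a correction.

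Protocol section 4.5 says that patients "receiving benz bromarone should be advised to drink water, and urine alkalinization should be considered if the patient's urine is acidic". No corresponding advice is stated for febuxostat. Section 5.2 (7) refers to early-morning urine and describes no timed collection. SAP 5.5.1 analyses secondary outcomes in the same way as the primary outcome, which under SAP 5.4 means an unpaired t-test or ANOVA between arms. Urine concentration is not taken into account.

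SAP 2-6-2 (6) specifies "Change in urine pH from immediately before initiation of randomized treatment (visit2) to 8 & 52 weeks", as both percent and absolute change.

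**The concern.** The concentration of a urinary marker depends on how much is excreted and on how much water it is excreted in. Dividing by creatinine from the same specimen is the usual way to remove the second factor, and the SAP does this for every other urinary marker with a concentration unit. It gives no reason for treating 8-OHdG differently.

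In many trials this would only add noise. Here the one stated piece of water advice is tied to allocation, so any dilution it causes would differ systematically between arms. Randomisation does not protect against it, because the advice follows allocation.

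Protocol section 1 says it is unknown whether lowering uric acid, inhibiting XO or inhibiting URAT1 slows CKD progression, and it names oxidative stress among the proposed mechanisms. An apparent fall in 8-OHdG with benzbromarone that was really dilution could be read as evidence about mechanism.

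**Working it through.** The documents give no SD, target difference or power for 8-OHdG, so there is no figure of the plan's own to reproduce. The check sets the provisions side by side and then illustrates the possible size.

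**Units of the urinary markers (SAP 2-6-2)**

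| Item | Marker | Absolute unit | Creatinine-corrected |
|---|---|---|---|
| (5) | albumin | mg/gCr | yes |
| (9) | 8-OHdG | ng/mL | no |
| (10) | angiotensinogen | µg/gCr | yes |
| (11) | L-FABP | µg/gCr | yes |

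**Does change from baseline remove dilution?** Let C0 be the concentration at visit 2, with excretion unchanged, and let urine volume in the later sample be higher by a fraction f. The later concentration is C0/(1+f).

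- Absolute change: C0/(1+f) − C0, which is below zero for any f above zero.
- Percent change: 1/(1+f) − 1, also below zero.

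Visit 2 is immediately before treatment, and the advice in section 4.5 applies to patients already receiving the drug. The baseline value would therefore not carry the dilution, and both versions of the endpoint are affected.

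**Possible size (f is assumed; the documents give none)**

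| Assumed extra volume f | Fall in ng/mL, 1 − 1/(1+f) |
|---|---|
| 10% | 1 − 1/1.10 = 9.1% |
| 20% | 1 − 1/1.20 = 16.7% |
| 30% | 1 − 1/1.30 = 23.1% |
| 40% | 1 − 1/1.40 = 28.6% |

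**Consequence for the test (a second assumption).** Take 50 per arm less the planned 20% dropout, 50 × 0.8 = 40 per arm, with two-sided 5% and no true effect on excretion. On the log scale the spurious difference is ln(1+f) and its standard error is s × √(2/40), where s is an assumed SD of the log change. For f = 20% and s = 0.5, ln(1.20) = 0.182 and the standard error is 0.112. The ratio is 1.63, which gives about a 37% chance of p < 0.05.

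| f | s = 0.3 | s = 0.5 | s = 0.7 |
|---|---|---|---|
| 10% | 30% | 13% | 9% |
| 20% | 78% | 37% | 21% |
| 30% | 97% | 65% | 39% |

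The nominal value is 5%. The spread across the table shows how far the result depends on the two assumptions.

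**After creatinine correction.** In one specimen 8-OHdG and creatinine are diluted by the same factor: [E/(1+f)] / [K/(1+f)] = E/K, where E and K are the undiluted concentrations. The factor cancels for every f, and with no true effect the error rate returns to 5%.

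**The case against.** The strongest reply is that no dilution difference is documented. Section 4.5 is advice, with no volume, adherence or urine-flow figure, and both tables above rest on assumed inputs. A reader might infer from the units and the advice that the endpoint is biased towards benzbromarone. The documents do not support that; they support only that it is open to such bias.

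A reader might also infer that febuxostat patients receive no water advice. That goes too far. Both arms receive lifestyle guidance, described by an open-ended list that points to a guideline not reproduced here. It may cover fluid intake, and because it begins in the run-in, part of any hydration effect could be shared and already present at visit 2. Early-morning sampling could also weaken the link between daytime drinking and the specimen. Both points stand, and both reduce the likely size.

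Nor can 8-OHdG safely be called the only oxidative-stress measure. Protocol section 5.2 (6) prints angiotensinogen and L-FABP under the same subheading. The section title names renal RA-system and tubulointerstitial markers separately, so subheadings may have been lost, but the printed list does not settle it.

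The unit may simply be a slip: item (1) of the same list labels an 8-week percent change as per 52 weeks. If so, the correction is still needed, because the SAP as written produces an analysis in ng/mL.

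Finally, this is one of eleven numbered secondary endpoints in a study whose SAP calls its main objective exploratory. It does not touch the eGFR result. That limits the importance of the point but does not answer it.

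**Conclusion.** The point holds as an avoidable weakness in one secondary endpoint. The SAP fixes 8-OHdG as an uncorrected concentration, unlike the other urinary markers, in a trial where the only stated water advice is for one arm. A dilution difference arising after visit 2 could produce or distort a between-arm difference with no change in excretion, and neither change from baseline nor percent change would remove it. The direction would be a larger apparent fall with benzbromarone.

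The size is unknown. The 9-29% fall is what an assumed 10-40% higher urine volume in the sample implies, with unchanged excretion and no shared hydration effect. The error rates also assume an SD for the log change.

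Urine pH is a separate and minor matter. One might conclude that its analysis is invalid because percent change on a logarithmic scale is hard to interpret, but absolute change is already specified alongside it. What remains is that alkalinisation is mentioned for benzbromarone patients only, so the pH contrast would include any such co-intervention.

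**What to change.** In SAP 2-6-2 (9), define the 8-OHdG endpoint per g (or mg) creatinine, as percent and absolute change, and keep ng/mL as a descriptive summary. Use the urinary creatinine already needed for the other per-gCr markers. Confirm first that it comes from the same specimen: protocol section 5.2 describes the frozen, batch-measured markers and the urinalysis separately, so this is likely but not stated. If ng/mL was a labelling slip, correct the label.

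For urine pH, name the absolute change as the summary for comparison, and add a sentence that the contrast includes any alkalinisation given to benzbromarone patients.

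The cost is a few words in the SAP and one division per sample. No new assay is needed if the specimen is confirmed to be the same. No change to treatment or to patient advice is involved.
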